**10.9 Pregnancy**

Pregnancy is considered an unanticipated event and pregnancy as well as its outcome must be documented and reported to overall PI and DSMC and Office of Research Integrity, as well the FDA and sponsor in according to reporting requirements. Any pregnancy occurring in a patient or patient's partner from the time of consent to 90 days after the last dose of study drug must be reported and then followed for outcome. Newborn infants should be followed until 30 days old.

## 11. STUDY CALENDAR

	Pre-Study	Day 1	Day 3 or 4	Day 7 +/-2 Days	Day 10 or 11	Day 14 +/- 4 Days	Day 28 +/- 4 Days	Day 40*** +/- 4 Days	
Investigational Agent (s) (section 6.0)		A							
Informed consent screening (optional)	X								
Informed consent treatment		X							
Demographics		X							
Eligibility review via medical record	X								
Medical history via medical record review		X				X	X	X	
In-person evaluation		X				X			
Telehealth contact			X a	X a	X a				
Concurrent meds		X-----X							
CBC w/diff, plts*		X				X*			
Serum chemistry, (CMP)*		X				X*			
EKG for QTc		X b				X	X****		
Adverse Events		X-----X							
Standard of Care Nasopharyngeal, Swab and SARS-CoV-2 antibody testing, if clinically indicated (optional)****						X**	X**	X**	
Sputum sample or OP swab (alternative)		X				X	X	X	
Blood sample for Inflammatory cytokines, D-Dimer, CRP, and Procalcitonin and seroconversion (10 mL and 6 mL purple tops)		X				X	X	X	
Blood sample for platelet studies (5 mL yellow top) (optional)		X**				X**	X**	X**	
CPT tube (8 mL speckled top)(optional)		X**				X**	X**	X**	
Saliva sample (optional)		X**				X**	X**	X**	

A - based on assigned arm

\*if not obtained for routine care (for screening phase, if not obtained within the previous 30 days; for treatment phase, if not obtained for routine care of COVID19)

\*\*optional

\*\*\* Day 40 only occurs if patient's serology is negative and viral RNA is positive

\*\*\*\*Only if indicated for routine care

a phone or telehealth contact if the patient is an outpatient

b EKG must be obtained within 5 days of registration

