### **1.2 Secondary Objectives**

- 1.2.1 To assess the decrease in viral load at Day 14.
- 1.2.2 To assess the development of severe respiratory or other organ failure in the study population
- 1.2.3 To assess progression to ICU care or ventilation in non-critically ill hospitalized patients and overall study population
- 1.2.4 To assess clearance of viral RNA by PCR testing at days 1, 14, 28, and 40 days
- 1.2.5 To assess mortality, clinical status of subject at Day 14, using the COVID 7-point ordinal outcomes scale, and rate of severe adverse events defined as grade 3 non hematologic or greater by DMID Toxicity Scale for Determining Severity of Adverse Events
- 1.2.6 To assess the safety, tolerability and compliance with each regimen.

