### **1.3 Exploratory Objectives**

- 1.3.1 To observe and record the impact of each drug combination on inflammatory markers (procalcitonin, D-Dimer, hs-CRP) and their potential prognostic/predictive value
- 1.3.2 To determine the rate and timeframe of SARS-CoV-2 seroconversion as a marker of acquired immunity via the presence of COVID-19 antibodies in RNA negative patients as a marker of acquired immunity using either a rapid diagnostic test (RDT) or enzyme-linked immunosorbent assay (ELISA) assay.
- 1.3.3 To determine if early detection of elevated inflammatory cytokines are predictive of severe infection or severe disease.
- 1.3.4 To perform post-hoc covariate adjusted analysis for potential pre-treatment, outcome-prognostic covariates such as age, sex, degree of illness, clinical chemistries, and timing of onset of symptoms relative to study inclusion.
- 1.3.5 To evaluate the effect of COVID-19 on platelet function to assess severe coagulation complications
- 1.3.6 To evaluate viral clearance at Day 14, 28 and 40

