- 2) Collection of medications, pill diary and instructions
- 3) Mobile EKG tracing (outpatients) or standard EKG (inpatients) to assess QTc interval
- 4) Correlative blood sample
- 5) Sputum sample, with OP swab (alternative, if no sputum available)
- 6) Saliva sample (optional)
- 7) Nasopharyngeal swab (optional and if indicated for standard of care)\*
- 8) COVID-19 ordinal scale assessment (See Appendix B)
- 9) Toxicity assessment via telehealth or phone call (+/-4 days)

Day 28 (+/- 4 days) visit will also be completed in clinic or inpatient hospital.

- 1) Correlative blood sample
- 2) Sputum sample, with OP swab (alternative, if no sputum available)
- 3) Saliva sample (optional)
- 4) Nasopharyngeal swab (optional and if indicated for standard of care)\*
- 5) Serology testing\*
- 6) COVID-19 ordinal scale assessment (See Appendix B)
- 7) Toxicity assessment via telehealth or phone call (+/-4 days)

Day 40 (+/- 4 days) visit. If serology testing is negative or viral load remains positive, patients will be requested to return for a Day 40 visit (optional) will also be completed via drive through (preferred), clinic or inpatient hospital.

- 1) Correlative blood sample
- 2) Sputum sample, with OP swab (alternative, if no sputum available)
- 3) Saliva sample (optional)
- 4) Nasopharyngeal swab (optional and if indicated for standard of care)\*
- 5) Serology testing (optional and if indicated for standard of care)\*
- 6) COVID-19 ordinal scale assessment (See Appendix B)

\*These are considered standard of care tests

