### 9.2 Secondary Endpoints

#### Secondary endpoints related to efficacy:

- Presence of symptoms or physical examination signs related to COVID-19 disease on Day 14 including: fever, shortness of breath, muscle aches, sore throat, loss of sense of taste or smell, etc.
- Presence of SARS-CoV-2 RNA as detected by polymerase chain reaction (PCR) in nasopharyngeal samples measured minimally on Days 1, 14 and 28
- Proportion of patients with symptoms or physical examination signs related to COVID-19 disease including shortness of breath, muscle aches, sore throat, loss of sense of taste or smell, hospital admission, length of stay, supplemental oxygen requirements, need for mechanical ventilation, intensive care unit admission, etc.

- Time to improvement and resolution of symptoms from baseline to Day 14 and 28
- Oxygen-free days to Day 28
- Ventilator-free days to Day 28
- Vasopressor-free days to Day 28
- ICU-free days to Day 28
- Hospital-free days to Day 28

#### Secondary endpoints related to safety and tolerability up to Day 28

- Incidence, severity, drug-relatedness, and seriousness of adverse events
- Proportion of patients meeting Hy's law criteria
- Proportion of patients with the following Liver function tests (LFT) changes:
  - Any ALT or AST  $\geq 5 \times$  ULN
  - Any AST or ALT  $\geq 3 \times$  ULN together with the appearance of fatigue, nausea, vomiting, right upper quadrant pain or tenderness, fever, rash and/or eosinophilia (eosinophil percent or count above the ULN)
  - Persistent ALT  $\geq 3 \times$  ULN for a period of more than 4 weeks.
- Proportion of patients with significant changes in ECG findings, including heart rate, ECG intervals (PR, QTcB, QTcF), conduction changes, or abnormalities including severe QTc prolongation of  $> 500$  ms.
- Proportion of patients with serious allergic and skin reactions
- Proportion of patients with severe hypoglycemia
- Proportion of patients with retinopathy or macular degeneration
- Proportion of patients with seizure
- Proportion of patients with acute pancreatitis
- Proportion of patients with acute kidney injury
- Proportion of patients with receipt of renal replacement therapy
- Proportion of patients with neutropenia, lymphopenia, anemia, or thrombocytopenia
- All-cause mortality rate

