## **12. MEASUREMENT OF EFFECT**

### **12.1 Evaluation of Response**

Subjects will be assessed for incidence of change in COVID 7-POINT ORDINAL OUTCOMES SCALE from the time of diagnosis to Day 14 (primary endpoint) and Day 28 (secondary endpoint). Subject sputum samples will be assessed for viral RNA by PCR on Day 1, 14, 28 (and where indicated at Day 40) in the [name] lab. Viral loads will be expressed in copies per mL and the decline in viral copy number will be assessed between Day 1, 14, 28 (and where indicated at Day 40) using SAS.

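### Section 4.9 and the study calendar give different triggers for the Day 40 visit; under the calendar rule an arm's Day 40 viral clearance cannot be recovered, and section 9.5 gives Day 40 no denominator

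*Combined protocol and SAP*

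**What the plan says.** Two current passages set the trigger for Day 40.

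- Section 4.9: "If serology testing is negative or viral load remains positive, patients will be requested to return for a Day 40 visit". The visit is marked optional.
- Section 11, calendar footnote: the visit is held only when a patient's "serology is negative and viral RNA is positive".

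Two objectives use Day 40 with no restriction to a subset.

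- Objective 1.2.4 (secondary): "To assess clearance of viral RNA by PCR testing at days 1, 14, 28, and 40 days".
- Objective 1.3.6 (exploratory): "To evaluate viral clearance at Day 14, 28 and 40".

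The measurement and analysis sections are narrower. Section 12.1 says "the decline in viral copy number will be assessed between Day 1, 14, 28 (and where indicated at Day 40) using SAS". The RNA endpoint in section 9.2 is "measured minimally on Days 1, 14 and 28". Section 9.5 names a clearance rate at Day 28 only, and its missing-data rule covers only the primary endpoint. No section says who is in the denominator at Day 40, or how patients who were not called back are counted.

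**The concern.** The two triggers recall different patients. Under *and*, a patient who is still shedding virus but has antibodies is not retested, and neither is one who has cleared but remains seronegative. Under *or*, both return.

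Either rule selects on Day 28 status, so clearance among those seen at Day 40 is not the arm's clearance at Day 40. With no stated denominator, an analyst could report the rate among attenders, count the unsampled as cleared, or carry Day 28 status forward, and get different answers from the same data. A secondary and an exploratory objective depend on that choice.

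The *and* rule also affects objective 1.3.2, on the timing of seroconversion in RNA-negative patients. Those who are RNA-negative and seronegative at Day 28 would not be recalled, so their later seroconversion would go unseen at Day 40.

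**Working it through.** The plan states no Day 40 figure, so there is none to reproduce. The check compares the two rules by expected values.

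**Inputs.** From the documents: 60 patients per arm (section 9.3) and the two triggers, read as applying to Day 28 status. The documents do not give the following, so they are assumed:

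- *c*, share RNA-negative at Day 28: 0.6 to 0.9
- *s*, share seropositive: 0.5 to 0.9, independent of RNA status
- *q*, chance of clearing by Day 40 if positive at Day 28: 0.5 to 0.7
- no rebound, and every patient called attends

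**Formulas.**

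- True Day 40 clearance: c + (1 − c)q
- Share sampled under *or*: (1 − c) + c(1 − s) = 1 − cs
- Share sampled under *and*: (1 − c)(1 − s)
- Clearance among those sampled under *or*: [c(1 − s) + (1 − c)q] / (1 − cs)
- Clearance among those sampled under *and*: q

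**Example: c = 0.8, s = 0.7, q = 0.5.**

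- Truth: 0.8 + 0.2 × 0.5 = 0.90
- *Or*: sampled 1 − 0.56 = 0.44, about 26 of 60. Clearance among them: (0.24 + 0.10) / 0.44 = 0.77
- *And*: sampled 0.2 × 0.3 = 0.06, about 4 of 60. Clearance among them: 0.50
- *And*, all unsampled counted as cleared: 1 − 0.06 × 0.5 = 0.97
- *And*, Day 28 status carried forward for the unsampled: 0.8 + 0.06 × 0.5 = 0.83
- *Or*, Day 28 negatives counted as cleared: 0.90, the true value

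Under *and*, the answer can only be placed between 0.83 and 0.97. That width of 0.14 is (1 − c)s = 0.2 × 0.7, the share of the arm that is RNA-positive, seropositive and never retested.

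**Over the assumed ranges.**

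| Quantity | *or* | *and* |
|---|---|---|
| Sampled per arm of 60 | about 11 to 42 | about 1 to 12 |
| Clearance among sampled | 0.57 to 0.95 | 0.50 to 0.70 |
| Unsampled counted as cleared | equals truth | 0.90 to 0.997 |

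True clearance runs from 0.80 to 0.97. In every combination the rate among those sampled is below the truth, and under *and* counting the unsampled as cleared is above it.

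**Can arms change order?** Under *and*, clearance among attenders equals q whatever c is. Under *or*, the derivative with respect to c has numerator (1 − s)(1 − q), which is never negative. Better Day 28 clearance alone therefore cannot make an arm look worse. Reversal needs q or s to differ as well. For example, under *and*, take arm A with c = 0.9, q = 0.3 (true 0.93) and arm B with c = 0.7, q = 0.5 (true 0.85). Attenders show 0.30 and 0.50.

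**The case against.** The strongest reply is that no section plans an all-patient Day 40 rate. Section 12.1 takes the Day 40 sample only where indicated, section 9.2 sets Days 1, 14 and 28 as the minimum, and section 9.5 summarizes clearance at Day 28. Section 9.1 adds that arms are not compared, and Day 40 feeds neither selection nor the interim rules. All of that stands. A reader might infer that the plan commits to a biased Day 40 estimate, but the documents support only the narrower statement: an unrestricted objective has no denominator, and one of its two sampling rules cannot serve it.

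Three other inferences go too far.

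- That attenders would show about 50% under either rule. That holds only under *and*; under *or*, cleared but seronegative patients also attend.
- That patients cleared by Day 28 are mostly absent under *or*. The absent share is the seropositive share among them, which the documents do not give.
- That an arm with better Day 28 clearance would look worse at Day 40. As shown above, this needs a further difference between arms.

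Section 9.5 also mentions longitudinal models for RNA over time. These do not rescue the *and* rule, because no RNA-positive, seropositive patient is ever observed at Day 40 and any estimate for them would be extrapolation.

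**Conclusion.** The contradiction is exact and lies in current text. Under the calendar rule, Day 40 clearance for an arm is not recoverable; in the example it is known only to lie between 0.83 and 0.97, and attenders show 0.50 against a true 0.90. Under the section 4.9 rule the gap among attenders is smaller (0.77 against 0.90) and can be closed with full attendance and no rebound, but the plan states neither condition and the visit is optional.

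The sizes rest on assumed clearance and seropositivity rates and on independence of serology and RNA status. The contradiction and the untested group under *and* do not. The consequence is minor: it is confined to objectives 1.2.4 and 1.3.6, with a side effect on 1.3.2. The Day 14 primary endpoint and the Day 28 clearance summary are untouched.

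**What to change.** 1. Reconcile section 4.9 and the calendar footnote to one trigger that retests every patient still RNA-positive at Day 28. The *or* wording does this and also keeps seronegative patients for objective 1.3.2. State which serology result counts: the calendar lists both an optional standard-of-care antibody test and a research blood sample for seroconversion.

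2. In section 9.5, choose one of two definitions:
   - cumulative Day 40 clearance over the whole analysis set, with Day 28-negative patients counted as cleared under a stated no-rebound assumption, observed Day 40 results used wherever they exist, and a rule for patients called who do not attend; or
   - a Day 40 objective restricted to the triggered subset and reported as such, with objectives 1.2.4 and 1.3.6 reworded to match.

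The first option leans on no rebound, which needs saying because section 2.7.1 names recrudescence as an interest.

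The cost is wording plus some optional visits. Relative to section 4.9 there are no extra visits. Relative to the calendar, full use of *or* adds about 23 per arm in the example (26.4 − 3.6 = 22.8). Retesting RNA-positive patients regardless of serology, and no others, would add about 8 to the calendar's number (0.14 × 60 = 8.4).

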## **12. MEASUREMENT OF EFFECT**

### **12.1 Evaluation of Response**

Subjects will be assessed for incidence of change in COVID 7-POINT ORDINAL OUTCOMES SCALE from the time of diagnosis to Day 14 (primary endpoint) and Day 28 (secondary endpoint). Subject sputum samples will be assessed for viral RNA by PCR on Day 1, 14, 28 (and where indicated at Day 40) in the [name] lab. Viral loads will be expressed in copies per mL and the decline in viral copy number will be assessed between Day 1, 14, 28 (and where indicated at Day 40) using SAS.

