## **2. BACKGROUND**

### **2.1 SARS-CoV-2 Background**

Coronavirus Disease 2019 (COVID-19) is a highly contagious disease, caused by a novel enveloped RNA beta-coronavirus, also known as severe acute respiratory syndrome coronavirus-2 (SARS-CoV-2). [1] The first case of this unprecedented outbreak “pneumonia of unknown

etiology” was reported in Wuhan City, Hubei Province, China on December 8th, 2019 and reported to the World Health Organization (WHO) on December 31st, 2019. [2] WHO declared a COVID-19 global emergency on January 30, 2020, and then categorized the outbreak as a pandemic on March 11, 2020. [3] As of April 22, 2020, more than 2,628,894 confirmed cases of COVID-19 worldwide and 182,740 people globally have died from COVID-19 since it emerged in China, according to the data from Johns Hopkins University.

While the majority of patients with COVID-19 develop mild or uncomplicated illness, approximately 20-30% of hospitalized patients have required intensive care support and 5% of those have multi-organ failure or shock. The case fatality rate ranges from 1 to 4% and it is higher among those with pre-existing comorbid conditions such as cardiovascular disease, diabetes mellitus, obesity, chronic respiratory disease, hypertension and cancer. [4] The vast majority of patients presents with fever (83-99%), cough (59-82%), fatigue (44-70%), anorexia (40-84%), shortness of breath (31-40%), sputum production (28-33%), myalgias (11-35%). [2, 5-9] Less than 10% of patients will present with headache, confusion, rhinorrhea, sore throat, hemoptysis, vomiting, or diarrhea. [2, 5, 6] Anosmia or ageusia preceding the onset of respiratory symptoms has been anecdotally reported. [10]

The Center for Disease Control and Prevention (CDC) from China divided the clinical manifestations of the disease as below: [4]

- Mild to moderate disease (81%): non-pneumonia and mild pneumonia
- Severe disease (14%): dyspnea, respiratory frequency  $\geq 30/\text{min}$ , blood oxygen saturation ( $\text{SpO}_2$ )  $\leq 93\%$ ,  $\text{PaO}_2/\text{FiO}_2$  ratio or P/F [the ratio between the blood pressure of the oxygen (partial pressure of oxygen,  $\text{PaO}_2$ ) and the percentage of oxygen supplied (fraction of inspired oxygen,  $\text{FiO}_2$ )]  $< 300$ , and/or lung infiltrates  $> 50\%$  within 24 to 48 hours
- Critical disease (5%): respiratory failure, septic shock, and/or multiple organ dysfunction or failure

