#### 4.9 Patient Registration to Treatment

To register a patient, the following information should be reviewed by the clinical research nurse (CRN) / clinical research associate (CRA) with the study physician per MCC SOPs to confirm eligibility:

- Copy of COVID19 testing results
- Mobile EKG tracing (outpatients) or standard EKG (inpatients) within 5 days of registration to assess QTc interval
- Eligibility labs, as well as correlative labs to be drawn
- Eligibility Checklist

Once eligibility is confirmed, the CRN/CRA will complete subject registration in the OnCore database (minimum data footprint) for randomization and complete study-required RedCap data forms. To complete the registration process, the CRN/CRA will:

- assign a patient study number
- register the patient on the study in OnCore
- receive the automated treatment arm assignment
- send an email or other communication to the study team of arm assignments.

If a patient is deemed ineligible for treatment their specimens will be retained in the COVID19 BIOBANK if the subject has indicated agreement to specimen collection and long-term storage in the consent form.

At the Day 1 visit or inpatient the following will be completed

- 1) Sign **treatment informed consent** (unless previously e-consented as above)
- 2) Undergo blood testing for eligibility (in subjects who have not had assessment of screening labs within the last 30 days will require blood draw)
- 3) Complete an eligibility questionnaire (age, concurrent diseases, current medications, contact information)
- 4) Undergo a mobile EKG or standard EKG tracing to assess QTc interval (within 5 days of registration)
- 5) Distribute medications, pill diary, and instructions
- 6) Baseline correlative blood sample
- 7) Sputum sample, with OP swab (alternative, if no sputum available)
- 8) Saliva sample
- 9) COVID-19 ordinal scale assessment (See Appendix B)
- 10) Limited visual physical exam unless a more complete exam is clinically indicated.

Day 3 or 4 phone call to assess clinical status and elicit concerns or questions.

Day 7 telehealth (+/- 4 days) is required for all patients to assess toxicity. If a subject has a standard of care telehealth visit during this period, this is also an acceptable toxicity assessment.

Day 10 or 11 phone call to assess clinical status and elicit concerns or questions

Day 14 (+/- 4 days) visit will also be completed in clinic or inpatient hospital.

- 1) Undergo blood testing for toxicity

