## 5. BIOMARKER, CORRELATIVE, AND SPECIAL STUDIES

### 5.1 Summary Table for Specimen Collection

Time Point	Specimen	Send Specimens To:
Archival		
	
 
• Discarded tissue or blood samples from original COVID19 testing
 
• Residuals from any of the research samples collected below
 
	Center for Clinical and Translational Science (CCTS) COVID-19 Research Registry and Specimen Bank (CRRSB)
Baseline – Day 1		
	
 
• 10 mL and 6 mL blood in EDTA (purple top) tubes for antibody testing, procalcitonin, CRP and cytokines
 
• 5 mL blood in ACD (yellow top) tube for platelet function assays (optional)
 
• 8mL blood in CPT tube (optional)
 
	Biospecimen Procurement and Translational Pathology Shared Resource Facility (BPTP SRF) or CCTS CRRSB

	
 
• Sputum sample (Mandatory) or OP swab (alternative, if sputum is unavailable)
 
• 1 ml of saliva (optional)
 
	
Day 14 (+/- 4 day)		
	
 
• 10 mL and 6 mL blood in EDTA (purple top) tubes for antibody testing, procalcitonin, CRP and cytokines
 
• 5 mL blood in ACD (yellow top) tube for platelet function assays (optional)
 
• 8mL blood in CPT tube (optional)
 
• Sputum sample (Mandatory) or OP swab (alternative, if sputum is unavailable)
 
• 1 ml of saliva (optional)
 
	BPTP SRF or CCTS CRRSB
Day 28(+/- 4 days)		
	
 
• 10 mL and 6 mL blood in EDTA (purple top) tubes for antibody testing, procalcitonin, CRP and cytokines
 
• 5 mL blood in ACD (yellow top) tube for platelet function assays (optional)
 
• 8mL blood in CPT tube (optional)
 
• Sputum sample (Mandatory) or OP swab (alternative, if sputum is unavailable)
 
• 1 ml of saliva (optional)
 
	BPTP SRF or CCTS CRRSB
Day 40(+/- 4 days)		
	
 
• 10 mL and 6 mL blood in EDTA (purple top) tubes for antibody testing, procalcitonin, CRP and cytokines
 
• 5 mL blood in ACD (yellow top) tube for platelet function assays (optional)
 
• 8mL blood in CPT tube (optional)
 
• Sputum sample (Mandatory) or OP swab (alternative, if sputum is unavailable)
 
• 1 ml of saliva (optional)
 
	BPTP SRF or CCTS CRRSB

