## **9.5 Statistical Analysis Plan**

The primary analysis will include estimate of the rate of stability in clinical scale (less than 2 point decrease in COVID 7-POINT ORDINAL SCALE) for each arm along with exact binomial 90% confidence interval. This is based on the first response in clinical scale after enrollment and randomization into the trial. In addition, the Bayesian posterior probability of the response rate being greater than 90% will be calculated for each arm at the end of the trial. The rates of development of severe respiratory or organ failure, clearance of viral RNA at day 28 and mortality will be summarized in each arm. Changes in SARS-CoV-2 RNA as detected by polymerase chain reaction (PCR) over time will be summarized in each treatment arm and compared using paired tests or longitudinal linear models.

Secondary endpoints related to proportion of outcomes as indicated in Section 9.2 will be estimated along with exact confidence intervals while descriptive statistics including median, range, IQR will be calculated for the duration in days of efficacy outcomes. Survival analysis methods will be utilized to estimate time to event endpoints. The exploratory and correlative endpoints such as inflammatory markers and cytokine levels will be summarized at baseline and follow-up time points. Changes from baseline will be compared using paired test or longitudinal linear mixed models.

Secondary analyses will include estimates of rate and confidence intervals of stability in clinical scale (less than 2 point decrease in COVID 7-POINT ORDINAL SCALE) either from the outpatient or inpatient continuum using subgroup analyses or logistic regression with a variable to account for response status among outpatients for each arm.

All patients who received study drugs will be included in the safety analysis. The maximum grade of toxicity for each category of interest will be recorded for each patient and summary results will be tabulated by category and grade. We will describe all serious ( $\geq$  grade 3) toxicity events. Frequency and incidence tables of toxicity and AEs will be generated in each treatment arm. Likewise, proportions of specific safety endpoints in Section 9.2 will be summarized.

m-ITT population is defined as all patients who have been randomized and received at least one dose of the study treatment. The primary analysis will be based on the m-ITT population.

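### The viral-load specimen can change between sputum and OP swab from visit to visit, and the analysis of change in copies per mL does not account for it

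*Combined protocol and SAP*

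**What the plan says.** Section 1.2 lists as a secondary objective "To assess the decrease in viral load at Day 14", alongside clearance of viral RNA. Section 12.1 gives the measure: "Viral loads will be expressed in copies per mL", and "the decline in viral copy number will be assessed between Day 1, 14, 28", with Day 40 where indicated. Section 9.5 states that changes in viral RNA will be summarised in each arm and "compared using paired tests or longitudinal linear models".

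The specimen is described differently in different places:

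- **Section 5.1** (Days 1, 14, 28 and 40): "Sputum sample (Mandatory) or OP swab (alternative, if sputum is unavailable". Section 4.9 repeats the fallback at each of these visits ("Sputum sample, with OP swab (alternative, if no sputum available"), and the Section 11 calendar allows either.
- **Section 5.3** reads as one OP swab and one sputum sample per patient at each time point, without calling the swab a fallback. The swab goes into viral transport media; no such step is given for sputum.
- **Section 9.2** defines presence of viral RNA on nasopharyngeal samples at Days 1, 14 and 28 as a minimum. In Section 4.9 that swab is optional at Days 14 and 28 and is not on the Day 1 list.
- **Section 12.1** names sputum only: "Subject sputum samples will be assessed for viral RNA by PCR on Day 1, 14, 28".
- **Section 2.7.1** has OP swabs or sputum evaluated in one laboratory by one qPCR assay.

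**The concern.** A within-patient change means something only if both measurements are on the same scale. Here the material can differ between Day 1 and Day 14 for the same patient. One is diluted in transport medium and the other, as far as the text says, is not, so a copy count per mL need not be the same quantity in both. Nothing in Section 9.5 or 12.1 keeps a patient on one specimen, adjusts for its type, or tests sensitivity to it.

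Switching need not be random. Section 2.1 lists sputum production among presenting symptoms, in 28-33% of patients. If the ability to give sputum changes as symptoms change, the specimen is linked to clinical course. That could affect the Day 14 viral-load objective and also the correlations that Section 2.7.1 plans between viral load, clinical status and time to resolution. Section 9.1 rules out comparisons between arms or with placebo, so each arm's own change is what will be read.

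**Working it through.** The plan states no effect size, standard deviation, power or specimen conversion for viral load, so there is no figure to reproduce. The check has two parts.

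**1. Can the plan, followed as written, mix specimens within a pair?**

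- The choice is made visit by visit (Sections 4.9, 5.1, 11).
- Both materials are used for viral load: Section 2.7.1 names both, and Section 5.3 describes both as collected for viral load.
- The contrast is within patient (Sections 9.5, 12.1), with no specimen term or restriction.

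So a Day 1 sputum value can be paired with a Day 14 swab value, or the reverse.

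**2. How large could the artefact be?** Every input here is an assumption; the documents give none of them. Working on the log10 scale (the plan does not name one), let

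- s = share of pairs switching from sputum to swab, minus the share switching the other way;
- d = log10 of (sputum reading / swab reading) at the same true viral load.

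With no true change, the spurious mean decline is s × d.

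For illustration, suppose 30% give sputum on Day 1 and half of them switch by Day 14, with none switching back: s = 0.30 × 0.5 = 0.15. With d from 0.5 to 1.5:

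- 0.15 × 0.5 = 0.075 log10
- 0.15 × 1.5 = 0.225 log10

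This is a factor of 10^0.075 = 1.19 to 10^0.225 = 1.68 in the geometric mean. Wider assumptions give (positive = false decline, negative = false rise):

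| Net switching s | d = -1 | d = 0 | d = 0.5 | d = 1 |
|---|---|---|---|---|
| 0.15 | -0.15 | 0 | 0.075 | 0.15 |
| 0.25 | -0.25 | 0 | 0.125 | 0.25 |
| 0.50 | -0.50 | 0 | 0.25 | 0.50 |

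Equal switching both ways, say 30% each, gives s = 0 and cancels on average.

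To put this against sampling noise, take 60 pairs per arm (the arm size in Section 9.3), a two-sided 5% paired test (assumed), one-way switching, and no true change. The chance of declaring a decline is approximately

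Φ( s·d / [√(SD² + s(1−s)d²) / √60] − 1.96 ).

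- s = 0.25, d = 0.5, SD = 1: 0.125 / (1.023 / 7.746) = 0.946; Φ(0.946 − 1.96) = 0.16.
- Over s = 0.25-0.50 and d = 0.5-1, the range is 0.16 to 0.93 for SD = 1 and 0.07 to 0.47 for SD = 2.

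Without the artefact this probability is 0.025. If every contrast uses one specimen type, the switching term is zero whatever d is.

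**The case against.** The strongest reply is that Section 12.1 names sputum only. Read literally, a patient without sputum has a missing value, not a distorted one. Section 5.3 can also be read as giving every patient an OP swab at every time point, in which case a matched series already exists. Neither Section 9.5 nor Section 12.1 actually says that the two materials are pooled. These points stand as far as they go. But the sputum-only reading conflicts with Sections 2.7.1, 5.1 and 5.3, and it would replace the problem with missing data that may depend on recovery. The favourable reading of Section 5.3 conflicts with the fallback wording in Sections 4.9 and 5.1. The text does not settle which applies.

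A reader might go further and infer that recovering patients will show a false viral decline. The documents do not support that. It needs sputum to read higher than swab and switching to run mainly from sputum to swab, and neither is stated. The 28-33% is a symptom frequency at presentation, not the share of trial patients able to give a sample, and no section says that producers stop as they recover. Sputum is the first choice and the swab a fallback, so the two are substitutable rather than freely interchangeable.

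A bias between arms, or spurious clearance, might also be inferred. The design makes no comparisons between arms, and Section 9.2 ties RNA presence to nasopharyngeal samples, so neither is established. Without a control, within-arm decline cannot be separated from natural course in any case.

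**Conclusion.** The concern holds in limited form. The plan allows specimen type to change within a patient and analyses change in copies per mL as though it did not. Viral-load change can therefore be confounded with specimen type, possibly in a way linked to recovery. The direction is not established. The size is about 0.08-0.23 log10 if net switching is 15% and sputum reads 0.5-1.5 log10 higher than swab; it is zero with no offset or balanced switching, and reversed with a negative offset. What needs no assumption is that Sections 5.1, 5.3, 9.2 and 12.1 disagree on the specimen. The primary ordinal-scale endpoint, the interim rules and the selection of an arm are unaffected; the impact is confined to secondary and exploratory viral endpoints.

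**What to change.** 1. Reconcile Sections 4.9, 5.1, 5.3, 9.2, 11 and 12.1 by naming one specimen for each viral endpoint.
2. Record specimen type at every visit on the case report form.
3. In Section 9.5, include specimen type as a visit-level covariate in the longitudinal model of viral load. This assumes a constant offset and may not fully separate specimen from recovery if the two move together, but it is better than no adjustment.
4. Report same-specimen pairs as a sensitivity analysis, stating that the restriction loses pairs and may itself select on recovery, since it conditions on a post-baseline event.
5. Confirm whether Section 5.3 means one OP swab per patient at every time point. If so, make that matched OP series the main change analysis; paired sputum and swab from the same visit would also let the offset be estimated directly.

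The cost of items 1 to 4 is wording, one data field and one model term. Item 5 adds no collection if Section 5.3 already means it. If it does not, the cost of extra swabs cannot be judged from the documents, because Section 5.2.1 does not list the kit contents. The number of pairs lost under item 4 also cannot be computed, since no rate of sputum unavailability is given.
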